10.1.3 Sensitivity analyses

The following sensitivity analyses are defined to assess the robustness of results on each primary endpoint versus assumptions used in the statistical model for the main estimators:

- The comparison between treatment and control will be performed by means of MI under MAR assumption instead of MNAR. MI will be implemented in two steps:
 - Intermittent missing data up to primary time point (Week 4 for Schirmer I test, and Week 12 for SANDE) will be imputed using MCMC methods assuming MAR. A separate imputation model will be used for each treatment arm. The imputation models will include the observed values (baseline and intermediate), gender, and age class as covariates. In case of non-convergence or non-estimability issues, a single model will be considered with treatment arm added as explanatory variable to the model.
 - The remaining missing values with a monotone missing data pattern will be imputed based on data of corresponding treatment group.
 - Each imputed dataset will be analyzed using observed and imputed data. Rubin's rule will be used for combining results to draw inference. The adjusted estimated treatment differences between cenegeerin and vehicle (difference in proportions for Schirmer's test and differences in means for SANDE) will be displayed together with the corresponding two-side 95% confidence intervals and p-values.
- A tipping point strategy will be used as a sensitivity analysis for missing data for assessment of superiority (if shown) of rhNGF for each endpoint. Tipping point analysis will assess how departures from MI under MNAR assumptions must be to overturn conclusions from the primary superiority analysis. Tipping point will be based on iterative application of MI. In the first iteration, MI-RD method is assumed as described in section 10.1.2. In successive iterations, the imputed values for the rhNGF arm are shifted by a constant to represent a worse effect in each iteration. This can be achieved by using the N completed datasets obtained under MI-RD and shift the imputed values. The tipping point is the shift at which the p-value becomes non-significant. Outline of tipping point:
 - Use MI-RD to impute missing values.
 - Assuming that the tipping point is between -10 and 0, the following actions will be performed for $\Delta = 0, -0.1, -0.2, -0.3, \dots, -10$:
 - Add Δ to the imputed values at the rhNGF arm.
 - Analyze the completed data sets using the same method outlined in section 10.1.2.
 - the plot of all p-values for Δ between -10 and 0 will be created.
 - based on the plot, the approximate value of the tipping point $T_{p\text{approx}}$ is identified considering a threshold for the p-values of 0.02500.
 - after identification of $T_{p\text{approx}}$, finest research of the tipping point will be performed in the range $T_{p\text{approx}} \pm 1$ by incrementing Δ of 0.01 and following the usual steps:
 - Add Δ to the imputed values at the rhNGF arm.
 - Analyze the completed data sets using the same method outlined in section 10.1.2.
 - The tipping point is the smallest Δ at which $p\text{-value} \geq 0.02500$.

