9.4.3.2. Sensitivity analyses

The following sensitivity analyses are defined to assess the robustness of results on each primary endpoint versus assumptions used in the statistical model for the main estimators :

- The comparison between treatment and control will be performed in the FAS population by means of MI under MAR assumption instead of missing not at random (MNAR). MI will be implemented in two steps:
 - Intermittent missing data up to primary time point (Week 4 for Schirmer I test, and Week 12 for SANDE) will be imputed using MCMC methods assuming MAR. A separate imputation model will be used for each treatment arm. The imputation models will include the observed values (baseline and intermediate), gender, and age class as covariates. In case of non-convergence or non-estimability issues, a single model will be considered with treatment arm added as explanatory variable to the model;
 - The remaining missing values with a monotone missing data pattern will be imputed based on data of corresponding treatment group.

Each imputed dataset will be analyzed using observed and imputed as described in section 9.4.3.1. Rubin's rule will be used for combining results to draw inference. The adjusted estimated treatment differences between cenegermin and vehicle (difference in proportions for Schirmer's test and

differences in means for SANDE) will be displayed together with the corresponding two-side 95% confidence intervals and p-values.

- A tipping point strategy will be used as a sensitivity analysis for missing data for assessment of superiority (if shown) of cenegeerin. For each coprimary endpoint, tipping point, will assess how departures from MI under MNAR assumptions must be in order to overturn conclusions from the primary superiority analysis. Tipping point will be based on iterative application of MI-RD (or MI under wash-out approach), where the imputed values for the cenegeerin arm are shifted at a constant Δ to represent a worse effect in each iteration. The tipping points are the smallest Δ s at which no statistical significance is shown ($p \geq 0.025$).

In addition, for each primary endpoint, the regression models detailed in section 9.4.3.1 will be performed for supportive purposes:

- by considering complete cases only (i.e. without considering patients with missing primary endpoint);
- on the PP set instead of FAS.

Details on sensitivity and supportive analyses will be provided in the SAP.

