4.7 Eligible eye

Assuming that all the inclusion/exclusion criteria are met in both eyes, the worse eye (eligible eye) will be determined at the baseline visit using a stepladder approach, as follows:

1. Schirmer’s Test: worse eye determined as eye with lower Schirmer I score.
2. NEI score: if Schirmer I score is the same in both eyes, worse eye will be determined by NEI score (cornea + conjunctival staining).

If all the above are identical, determination of the worse eye will be based on the investigator’s judgement, otherwise the right eye will be used as the eligible eye.

5. Sample size justification

The sample size of the study is calculated based on results from previous studies.

Sample size was calculated according to the following assumptions:

- randomization ratio 1:1.
- a difference of 30% in Schirmer I rate of responders (value >10mm/5min at week 4.) in favor of rhNGF treatment at Week 4, with a responder rate of 5% for vehicle.
- 15 points in Global SANDE score improvement at Week 12, with a standard deviation of 20 points.

Based on these assumptions, a total sample size of 90 evaluable patients (100 pts considering 10% of patients not evaluable after enrollment) allows to achieve an overall power of 90% to show superiority of rhNGF eye drops solution vs vehicle in terms of both co-primary endpoints, considering a one-sided alpha of 0.025. Specifically:

- A power of 95.8% is achieved for Schirmer I primary endpoint.
- A power of 94.0% is achieved for SANDE primary endpoint.

6. Randomization and blinding

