15.5 SAS Code for the primary analysis

15.5.1 Schirmer I test >10mm/5min at week 4

Standard	Alternative code in case of no convergence
<pre> PROC MI DATA= EFFICACY01 NIMPUTE=200 SEED=820520 OUT=EFFICACY_MONO1; VAR BASVAL SCHIRMER_W2 AVAL; MCMC CHAIN=SINGLE NBITER=200 NITER=100 IMPUTE=MONOTONE; WHERE TRT=1; RUN; PROC MI DATA=EFFICACY01 NIMPUTE=200 SEED=820520 OUT=EFFICACY_MONO2; VAR BASVAL SCHIRMER_W2 AVAL; MCMC CHAIN=SINGLE NBITER=200 NITER=100 IMPUTE=MONOTONE; WHERE TRT=2; RUN; DATA EFFICACY_MONO; SET EFFICACY_MONO1 EFFICACY_MONO2; RUN; </pre>	<pre> PROC MI DATA= EFFICACY01 NIMPUTE=200 SEED=820520 OUT=EFFICACY_MONO; VAR BASVAL TRT SCHIRMER_W2 AVAL; MCMC CHAIN=SINGLE NBITER=200 NITER=100 IMPUTE=MONOTONE; RUN; </pre>
<pre> PROC SORT; BY _IMPUTATION_ SUBJID; RUN; </pre>	
<pre> PROC MI DATA=EFFICACY_MONO SEED=200582 NIMPUTE=1 OUT=EFFICACY_IMP; BY _IMPUTATION_; CLASS TRT AGE SEX EOTSTT; MONOTONE REG(AVAL = TRT AGE SEX BASVAL / DETAILS); MNAR MODEL(AVAL / MODELOBS= (EOTSTT='NOT COMPLETED')); VAR TRT AGE SEX BASVAL SCHIRMER_W2 AVAL; RUN; </pre>	<pre> PROC MI DATA=EFFICACY_MONO SEED=200582 NIMPUTE=1 OUT=EFFICACY_IMP; BY _IMPUTATION_; CLASS TRT AGE SEX EOTSTT; MONOTONE REG(AVAL = TRT AGE SEX BASVAL / DETAILS); MNAR MODEL(AVAL / MODELOBS= (TRT=2 /*Vehicle*/)); VAR TRT AGE SEX BASVAL SCHIRMER_W2 AVAL; RUN; </pre>

Standard	Alternative code in case of no convergence
<pre> DATA EFFICACY_IMP; SET EFFICACY_IMP; IF AVAL>10 THEN AVALC='Y'; ELSE AVALC='N'; RUN; ODS OUTPUT DIFFS=GLIMMIX_DIFFS; ODS OUTPUT PARAMETERESTIMATES=ESTIMATES; PROC GLIMMIX DATA=EFFICACY_IMP METHOD = QUAD; BY _IMPUTATION_; CLASS TRT(REF="1") AGE(REF="<=XX") SEX(REF="F") SITEID; MODEL AVALC(EVENT='Y')=TRT AGE SEX BASVAL /S DIST=BINARY LINK=LOGIT OR; RANDOM INTERCEPT / SUBJECT=SITEID; LSMEANS TRT / ILINK ODDSRATIO CL DIFF; RUN; ODS OUTPUT PARAMETERESTIMATES=POOLED_ESTIMATES; PROC MIANALYZE PARMS = ESTIMATES ; CLASS TRT AGE SEX; MODELEFFECTS INTERCEPT TRT AGE SEX BASVAL ; RUN; ODS OUTPUT PARAMETERESTIMATES=POOLED_DIFFS; PROC MIANALYZE DATA = GLIMMIX_DIFFS ; MODELEFFECTS ESTIMATE; STDERR STDERR; RUN; DATA POOLED_ODDS_RATIO; SET POOLED_DIFFS; ODDSRATIO=EXP(ESTIMATE); ODDS_95LL=EXP(LCLMEAN); ODDS_95UL=EXP(UCLMEAN); RUN; </pre>	

15.5.2 Change from baseline in the global SANDE score at week 12

Standard	Alternative code in case of no convergence

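### The Schirmer tipping-point analysis cannot go beyond all missing cenegermin patients being non-responders, and it never stresses the missing vehicle patients

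*SAP*

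**What the plan says.** SAP 10.1.3 applies one tipping-point recipe to both co-primary endpoints. It imputes the missing values, adds a constant Δ running from 0 to -10 in steps of 0.1, repeats the analysis of section 10.1.2, and looks for the Δ at which p reaches 0.025. Only one arm moves: "the imputed values for the rhNGF arm are shifted by a constant to represent a worse effect in each iteration". Protocol 9.4.3.2 also shifts the cenegermin arm alone.

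The Schirmer endpoint is binary. The code in SAP 15.5.1 imputes the value in millimetres and then classifies it: "IF AVAL>10 THEN AVALC='Y'; ELSE AVALC='N'". Section 10.1.3 does not say whether Δ is added before or after this cut. A shift in steps of 0.1 has meaning only on the millimetre scale, so shift-then-cut is the natural reading, but it is an inference.

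On the starting point, the SAP says: "In the first iteration, MI-RD method is assumed as described in section 10.1.2". The protocol is wider: "Tipping point will be based on iterative application of MI-RD (or MI under wash-out approach"). SAP 10.1.2.1 allows a fallback to Copy Reference (vehicle-based) imputation if there are too few retrieved dropouts. The list of changes from the protocol in SAP 7.9 does not mention the tipping-point analysis.

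**The concern.** The stated aim is to find how far the imputation assumptions must be wrong before the superiority conclusion is overturned. On a continuous endpoint, a one-arm shift can always be pushed until it does so. On an endpoint cut at 10 mm it cannot: once every imputed cenegermin value is at or below 10 mm, further shifting changes nothing. If the result is still significant there, the analysis reports no tipping point.

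The other way to lose the result is for missing vehicle patients to have responded more often than imputed, and the shift does not explore it. With few vehicle responders expected, a handful of such patients moves the comparison materially. Both co-primary endpoints must succeed, so a report of no tipping point for Schirmer would support the superiority claim while only one side of the missing data had been tested.

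**Working it through.** **Inputs from SAP section 5.** Allocation: "randomization ratio 1:1". Test level: "considering a one-sided alpha of 0.025". Rates: "a difference of 30% in Schirmer I rate of responders", "with a responder rate of 5% for vehicle", so 35% v 5%. There are 90 evaluable patients of 100, so 45 of 50 per arm, which I take as 5 missing per arm.

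**The plan's own figure.** Pooled-variance power with 45 per arm:

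(0.30√45 - 1.96√(2×0.20×0.80)) / √(0.35×0.65 + 0.05×0.95) = (2.012 - 1.109)/0.524 = 1.723, so power is 95.8%, as stated. The inputs are read correctly.

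**Where the shift starts and ends.** If imputed values are normal with mean m and SD s, the share above 10 mm after the shift is Φ((m + Δ - 10)/s). The documents give no Schirmer SD and no responder rate for retrieved dropouts, so I assume s = 3, 5 or 8 mm and a starting share of 5% (vehicle-like) or 35% (design rate).

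- *Starting at 5%:* 5 × 0.05 = 0.25 expected responders among the 5 missing. The share falls below 1% at Δ = -2.0, -3.4 or -5.5 (s = 3, 5, 8). The whole grid can lower the cenegermin rate only from 0.9×35% + 0.1×5% = 32.0% to 0.9×35% = 31.5%.
- *Starting at 35%, s = 5:* 35% at Δ = 0, 28% at -1, 22% at -2, 16% at -3, 8% at -5, 0.9% at -10. The decline is gradual. At most 5 × 0.35 = 1.75 expected responders are lost.

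**What the two approaches find.** The base case has 2/45 observed vehicle responders (close to 5%). The one-arm result comes from a simulation with 200 imputations combined by Rubin's rules, with missing vehicle values imputed at 5%. The two-way result sets all 5 missing cenegermin patients to non-responder and adds responders among the 5 missing vehicle patients. The test is the unadjusted logistic Wald test:

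z = ln[a(50-b) / (b(50-a))] / √(1/a + 1/(50-a) + 1/b + 1/(50-b)).

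Example, 12/50 v 5/50: ln(12×45/(5×38)) = 1.045; SE = √(1/12 + 1/38 + 1/5 + 1/45) = 0.576; z = 1.81; one-sided p = 0.035.

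| Cenegermin observed | p at end of one-arm shift | Missing vehicle responders needed | Tipped table | p |
|---|---|---|---|---|
| 9/45 | 0.025–0.029 (tips) | 1 | 9/50 v 3/50 | 0.039 |
| 10/45 | 0.018 | 2 | 10/50 v 4/50 | 0.047 |
| 11/45 | 0.012 | 2 | 11/50 v 4/50 | 0.030 |
| 12/45 | 0.0075 | 3 | 12/50 v 5/50 | 0.035 |
| 13/45 | 0.005 | 4 | 13/50 v 6/50 | 0.040 |
| 14/45 | 0.003 | 4 | 14/50 v 6/50 | 0.0255 |
| 15/45 | 0.002 | 5 | 15/50 v 7/50 | 0.029 |
| 16/45 | below 0.025 | none of 5 suffices | 16/50 v 7/50 | 0.018 |

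**Sensitivity to the assumptions.**

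- With a pooled z-test, the counts for 11/45 and 14/45 each rise by one (p just under 0.025 at the counts shown: 0.02497 and 0.0228). The range of 2 to 5 is unchanged.
- With 5/45 vehicle responders, the results that do not tip one-way but do tip two-way run from 14/45 to 19/45.
- With 10 missing per arm (twice the planned rate) and 2/40 vehicle responders, they run from 10/40 to 21/40. This includes the design rate, 14/40, where 4 missing vehicle responders suffice.

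**The case against.** A reader might infer that the shift saturates almost at once. That holds if imputed values look like vehicle values, under Copy Reference or with poorly responding retrieved dropouts. It is not a property of the plan. The first-choice imputation has treatment arm as a covariate, so cenegermin values need not be vehicle-like, and the 35% start above declines across most of the grid.

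A reader might also infer that the analysis can never find a tipping point, whatever the data. It can: 9/45 v 2/45 crosses 0.025, and 8/45 v 2/45 with 35% imputation goes from about 0.022 to 0.042. Conversely, at 16/45 with 5 missing per arm, finding none would be correct.

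The tipped allocations are also demanding. At 12/45, 3 of 5 missing vehicle patients must respond when 2 of 45 observed ones did, while none of 5 missing cenegermin patients responds. If one of those does, 13/50 v 5/50 gives p = 0.022 and the result stands. This objection is fair, but judging plausibility is the purpose of a tipping analysis, and the plan never displays these cells.

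It can further be said that shifting the active arm alone is what the protocol pre-specifies, that its floor answers a useful question, and that missing-at-random, complete-case and per-protocol analyses accompany it. All true, but none of them deliberately stresses the missing vehicle outcomes.

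Finally, a reader might conclude that the analysis cannot run if MI-RD fails. The documents do not go that far: the protocol names the wash-out alternative, and SAP 10.1.3 points to section 10.1.2, which contains Copy Reference. It is a wording gap.

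**Conclusion.** The concern holds in a limited form. For the Schirmer endpoint the one-arm shift stops at the all-non-responder floor, may start near it, and leaves missing vehicle responders unexamined. In the base case, results from 10/45 to 15/45 would be reported without a tipping point although 2 to 5 missing vehicle responders, with missing cenegermin patients as non-responders, would overturn them.

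This rests on the inferred order of shift and cut, on 5 missing per arm, on 2/45 vehicle responders, and on p-values without covariates, the site effect or, in the two-way cells, imputation variance. The boundaries are therefore approximate. The point concerns a sensitivity analysis; the documents give no ground for reading it as a fault in the primary test or as showing the one-arm shift to be invalid.

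**What to change.** Keep the one-arm shift and state in SAP 10.1.3 that, for Schirmer, Δ is added in millimetres before the 10 mm cut. Add a two-way tipping table for this endpoint: responders among missing cenegermin patients (from all down to none) by responders among missing vehicle patients (from none up to all). Analyse each cell with the primary model and mark the boundary where one-sided p reaches 0.025. The table needs no assumed Schirmer SD, and the one-arm floor can be located in it.

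Align SAP 10.1.3 with Protocol 9.4.3.2 so that the tipping analysis starts from MI-RD or Copy Reference, whichever the primary analysis used.

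The cost is some SAP wording, modest programming and one extra table. Some extreme cells will be implausible, and the report should say so when it interprets the boundary.

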10.1 Analysis of primary efficacy endpoint

10.1.1 Testing strategy and multiplicity adjustment

The following null hypothesis is defined on the first primary endpoint: the proportion of patients reaching a value of Schirmer I test (without anesthesia) $>10\text{mm}/5\text{min}$ at week 4 in cenegegermin (rhNGF) is lower or equal than control:

$$H_{01}: T_{\text{rhNGF}} \leq T_{\text{CONTROL}}$$

$$H_{11}: T_{\text{rhNGF}} > T_{\text{CONTROL}}$$

where T_{rhNGF} and T_{CONTROL} are the proportion of patients reaching a value of Schirmer I test (without anesthesia) $>10\text{mm}/5\text{min}$ at week 4 for cenegegermin and control groups, respectively. The null hypothesis H_{01} will be rejected if the associated primary analysis p-value will be lower than 0.025.

Similarly, the following null hypothesis is defined on the co-primary endpoint: the change from baseline (reduction) in the global SANDE score at week 12 in cenegegermin is lower or equal than control:

$$H_{02}: \mu_{\text{rhNGF}} \leq \mu_{\text{CONTROL}}$$

$$H_{12}: \mu_{\text{rhNGF}} > \mu_{\text{CONTROL}}$$

where μ_{rhNGF} and μ_{CONTROL} are the change from baseline (reduction) in the global SANDE score at week 12 for cenegegermin and control groups, respectively. The null hypothesis H_{02} will be rejected if the associated primary analysis p-value will be lower than 0.025.

Both null hypotheses H_{01} and H_{02} must be rejected to claim superiority of cenegegermin over control. Consequently, no multiplicity correction of type I error will be applied on primary endpoints analysis.

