If there are not enough retrieved dropouts for convergence of MI-RD regression model, a reference-based Multiple Imputation (MI) approach will be adopted to consider a missing not at random (MNAR) mechanism for missing data: imputation of values in the rhNGF arm (above step #2) will be done using the non-missing values from the control group (this approach will be referred as "Copy Reference"). This approach does not assume benefits for rhNGF in case of discontinuation and limits a post-discontinuation clinical effect to that of vehicle. The final decision on the use of the MI-RD vs Copy-Reference for this endpoint will be done at the time of the analysis and reported in the CSR.

Whether for MI-RD or Copy-Reference approach, the adjusted estimated treatment differences in proportions between cenegegermin and vehicle at week 4 will be displayed together with the corresponding two-side 95% confidence intervals and p-value.

10.1.2.2 Change from baseline in the global SANDE score at week 12

This co-primary endpoint will be analyzed by means of an Analysis of Covariance (ANCOVA) adjusting by pre-defined baseline factors (gender, age class, baseline global SANDE score as fixed effects and site as random effect) and a one-sided test will be used to test for differences between treatment groups. Rules for derivation of SANDE scores are reported in section 12.2.

For the imputation of missing data, a regression model will be created by including the baseline global SANDE score, gender, age class, and intermediate global SANDE scores up to week 12. Two hundred data sets will be generated, and the random seed number will be 37103939. MI will be implemented in the following steps:

1. Partial imputation assuming MAR will be carried out to impute intermittent (non-monotone) missing data of global SANDE score based on a multivariate joint Gaussian imputation model using the MCMC method. A separate imputation model will be used for each treatment arm. In case of non-convergence or non-estimability issues, a single imputation model will be considered (with treatment arm added as explanatory variable to the model). A total of 200 datasets will be created. These datasets will be utilized in Step #2.
2. The remaining monotone missing data will be imputed using a MI regression including the same explanatory variables of the previous step. According to MI-RD approach, only non-missing values from retrieve dropouts will be used to inform the regression model.

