12.1 Variable derivation

Table 3: Variable derivation rules

Parameter	Calculation
Screened	A patient is considered screened if (s)he has “Has written Informed Consent been obtained?” = Yes AND “Date of Informed Consent Signature at screening” filled
Screening failure	A patient is considered screening failure if (s)he has “Screen Failure date” filled
Enrolled	A patient is considered enrolled if (s)he has been screened and (s)he is not a screening failure.
Eligible eye	Assuming that all the inclusion/exclusion criteria are met: 
• If only one eye fulfills the criteria of Severe Sjögren's Dry Eye (“Which eye is diagnosed with Severe Sjögren's Dry Eye?” is answered with “Right Eye” or “Left Eye”) than the selected eye will be the “eligible eye”.• If both eyes fulfill the criteria of Severe Sjögren's Dry Eye (“Which eye is diagnosed with Severe Sjögren's Dry Eye?” is answered with “Both”) than the eligible eye will be selected according to the following rank:
i. the eye with lower Schirmer I score, otherwiseii. the eye with worse NEI score (cornea+conjunctival staining), otherwiseiii. the eye with worse investigator's judgement (“Were there any clinically significant abnormalities noted?” Equal to yes for a specific eye), otherwiseiv. the right eye.
Change from baseline	Each change from baseline will be defined as difference between the value at each post-baseline assessment and the baseline value.
Time since first diagnosis of Dry Eye	Randomization date - Date of diagnosis for eligible eye + 1

Parameter	Calculation
Time since first diagnosis of Severe Sjögren's Dry Eye	Randomization date - Date of diagnosis of Severe Sjögren's Dry Eye for eligible eye + 1
Total number of drops in the eligible eye taken during the treatment period	Sum of Morning/Afternoon/Evening Number of times the IMP has been administered for the eligible eye between Randomization visit date and End of Treatment date, considering 1 drop each time (morning, afternoon, evening). (from the eCRF form "IMP Administration" forms)
Total number of drops in the eligible eye scheduled during the treatment period	3*(Date of End of Treatment visit – Date of Randomization + 1) – (assessments not done on Randomization visit + assessments not done on End of Treatment visit)
The extent of exposure (days)	Date of last administration of IMP – Date of first administration of IMP + 1

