12.2 SANDE derivation

The SANDE questionnaire is comprised of two questions:

- How often do your eyes feel dry and/or irritated?
- How severe you feel your symptoms of dryness and/or irritation are?

This questionnaire uses a 100 mm horizontal line for each question to assess ocular discomfort and/or dryness experienced by the patients. In the SANDE questionnaire, frequency of symptoms ranges from “rarely” to “all of the time” and the severity of symptoms ranges from “very mild” to “very severe”. Patients are asked to place a mark on the two given lines based on the extent of their symptoms.

The locations of the marks made by the patients on the 100 mm horizontal lines will be measured in mm from left to right and recorded as frequency and severity score, respectively.

The global SANDE score will be calculated by multiplying the frequency score by the severity score and obtaining the square root.

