<pre> PROC MI DATA= EFFICACY01 NIMPUTE=200 SEED=37103939 OUT=EFFICACY_MONO1; VAR BASVAL SANDE_W2 SANDE_W4 SANDE_W8 AVAL; MCMC CHAIN=SINGLE NBITER=200 NITER=100 IMPUTE=MONOTONE; WHERE TRT=1; RUN; PROC MI DATA=EFFICACY01 NIMPUTE=200 SEED=37103939 OUT=EFFICACY_MONO2; VAR BASVAL SANDE_W2 SANDE_W4 SANDE_W8 AVAL; MCMC CHAIN=SINGLE NBITER=200 NITER=100 IMPUTE=MONOTONE; WHERE TRT=2; RUN; DATA EFFICACY_MONO; SET EFFICACY_MONO1 EFFICACY_MONO2; RUN; </pre>	<pre> PROC MI DATA= EFFICACY01 NIMPUTE=200 SEED=37103939 OUT=EFFICACY_MONO; VAR BASVAL TRT SANDE_W2 SANDE_W4 SANDE_W8 AVAL; MCMC CHAIN=SINGLE NBITER=200 NITER=100 IMPUTE=MONOTONE; RUN; </pre>
<pre> PROC SORT; BY _IMPUTATION_ SUBJID; RUN; </pre>	
<pre> PROC MI DATA=EFFICACY_MONO SEED=200582 NIMPUTE=1 OUT=EFFICACY_IMP; BY _IMPUTATION_; CLASS TRT AGE SEX EOTSTT; MONOTONE REG(AVAL = TRT AGE SEX / DETAILS); MNAR MODEL(AVAL / MODELOBS= (EOTSTT='NOT COMPLETED')); VAR TRT AGE SEX BASVAL SANDE_W2 SANDE_W4 SANDE_W8 AVAL; RUN; </pre>	<pre> PROC MI DATA=EFFICACY_MONO SEED=200582 NIMPUTE=1 OUT=EFFICACY_IMP; BY _IMPUTATION_; CLASS TRT AGE SEX EOTSTT; MONOTONE REG(AVAL = TRT AGE SEX / DETAILS); MNAR MODEL(AVAL / MODELOBS= (TRT=2 /*Vehicle*/)); VAR TRT AGE SEX BASVAL SANDE_W2 SANDE_W4 SANDE_W8 AVAL; RUN; </pre>

Standard	Alternative code in case of no convergence
<pre>ODS OUTPUT DIFFS=DIFFS; ODS OUTPUT PARAMETERESTIMATES=ESTIMATES; PROC MIXED DATA=EFFICACY_IMP; BY _IMPUTATION_; CLASS TRT(REF="1") SEXC(REF="F") SITEID; MODEL AVAL=TRT AGE SEXC BASVAL /S; RANDOM INTERCEPT / SUBJECT=SITEID; LSMEANS TRT / CL DIFF; RUN; ODS OUTPUT PARAMETERESTIMATES=POOLED_ESTIMATES; PROC MIANALYZE PARMS = ESTIMATES ; CLASS TRT SEXC; MODELEFFECTS INTERCEPT TRT AGE SEXC BASVAL ; RUN; ODS OUTPUT PARAMETERESTIMATES=POOLED_DIFFS; PROC MIANALYZE DATA = DIFFS ; MODELEFFECTS ESTIMATE; STDERR STDERR; RUN;</pre>

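### The single tipping-point grid (Δ from 0 to −10) moves SANDE in cenegermin's favour on the SAP's own definition of change, and the sign of the SANDE analysis variable is left in conflict

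*SAP*

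**What the plan says.** SAP 10.1.3 plans a tipping-point analysis for each co-primary endpoint if superiority is shown. Its stated principle is that "the imputed values for the rhNGF arm are shifted by a constant to represent a worse effect in each iteration". The outline that follows is common to both endpoints: "Assuming that the tipping point is between -10 and 0, the following actions will be performed for" Δ = 0, −0.1, …, −10, with Δ added to the imputed values in the cenegermin arm. Next, "based on the plot, the approximate value of the tipping point" is identified against a p-value threshold of 0.025, and a finer search runs within ±1 of it. There is no SANDE-specific grid, although SANDE has its own table (14.2.2.4) and figure (14.2.3.6). Protocol 9.4.3.2 also asks for shifts towards a worse effect but fixes neither grid nor sign.

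Four places bear on the direction of SANDE:

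- **SAP 12.2:** "The locations of the marks made by the patients on the 100 mm horizontal lines will be measured in mm from left to right", with severity running from very mild to very severe. Higher is worse.
- **SAP 10.1.2.2:** the first imputation step is to "impute intermittent (non-monotone) missing data of global SANDE score". The imputed quantity is the score itself.
- **SAP 12.1, Table 3:** "Each change from baseline will be defined as difference between the value at each post-baseline assessment and the baseline value". No exception is made for SANDE, so benefit is negative.
- **SAP 10.1.1:** the null hypothesis concerns "the change from baseline (reduction) in the global SANDE score at week 12", and the alternative is μ(rhNGF) > μ(control), so benefit is positive.

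The SANDE code in 15.5.2 ends in "MODEL AVAL=TRT AGE SEXC BASVAL /S" without defining AVAL.

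**The concern.** A tipping-point analysis shows how pessimistic the assumption about missing cenegermin patients must become before the conclusion fails. That works only if each step makes those patients worse. One negative grid cannot do this for two endpoints that point in opposite clinical directions, unless SANDE is first recoded so that higher is better.

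If the outline is programmed on the raw score or on the Table 3 change, each step credits the imputed cenegermin patients with fewer symptoms. The p-value then moves away from 0.025, the plot offers no approximate tipping point, and the ±1 search has nothing to start from. The report would show no tipping point for SANDE, and a reader would take that as robustness. This is the only planned analysis that stresses the missing-data assumption step by step until a co-primary conclusion fails.

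**Working it through.** **1. Direction of Δ under each possible coding**

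| Analysis variable | Source | Benefit appears as | Effect of negative Δ on cenegermin |
|---|---|---|---|
| Schirmer I, raw value | 15.5.1 (responder if AVAL > 10) | higher | worse, as intended |
| SANDE, week-12 global score | 10.1.2.2; AVAL follows baseline and the week 2, 4 and 8 scores in the 15.5.2 variable list | lower | better |
| SANDE, post-baseline minus baseline | Table 3 | more negative | better |
| SANDE, baseline minus week 12 | implied by 10.1.1 only | higher | worse |

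The grid is adverse for SANDE in the last row only, and no derivation or code creates that variable.

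**2. The plan's own SANDE power.** Section 5 of the SAP gives a difference of 15, SD 20, 90 evaluable patients (45 per arm) and one-sided alpha 0.025. The noncentrality is 15 / (20 × √(2/45)) = 3.558 on 88 df, and the power is 94.04%. This matches the stated 94.0%, so SD 20 is carried forward.

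**3. Effect of the grid on the Table 3 sign.** Assumptions: 50 per arm (100 enrolled, 1:1), a pooled t-test on 98 df, and a fraction f of the cenegermin arm imputed. The SAP gives only 10% not evaluable, so f = 0.10 and 0.20 are assumed. For an observed benefit D:

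- difference = −D + f × Δ
- cenegermin variance = 400 + (50/49) × f × (1 − f) × Δ²
- SE = √[(cenegermin variance + 400) / 50], which is 4.0 at Δ = 0

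Example with D = 10 and f = 0.10. At Δ = 0, t = −10/4.0 = −2.50 and one-sided p = 0.0070. At Δ = −10 the difference is −11, the variance 409.18 and the SE 4.023, so t = −2.734 and p = 0.0037.

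| Observed effect | p at Δ = 0 | p at Δ = −10, f = 0.10 | p at Δ = −10, f = 0.20 |
|---|---|---|---|
| 10 | 0.0070 | 0.0037 | 0.0019 |
| 8.5 | 0.0181 | 0.0101 | 0.0054 |

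In 0.1 steps from 0 to −10, p fell at every step for f = 0.05, 0.10, 0.20 and 0.30 at effects of 15, 10 and 8.5.

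**4. Where the result would tip with the sign corrected.** Solving for p = 0.025 with positive Δ:

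| Observed effect | 50/arm, f = 0.10 | 50/arm, f = 0.20 | 45/arm, f = 0.10 | 45/arm, f = 0.20 |
|---|---|---|---|---|
| 15 | +57.0 | +31.5 | +53.4 | +29.5 |
| 10 | +19.0 | +9.9 | +15.1 | +7.8 |
| 8.5 | +5.5 | +2.8 | +1.2 | +0.6 |

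Check for D = 10, f = 0.10, Δ = 19: difference −10 + 1.9 = −8.1, variance 433.15, SE 4.082, t = −1.984, p = 0.025.

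**5. Is reversing the sign enough?** At 50 per arm the smallest significant effect is 1.984 × 4.0 = 7.94 points. A grid from 0 to +10 finds a tip only for observed effects from 7.94 up to about 8.98 (f = 0.10) or 10.02 (f = 0.20). In 1,500 simulated trials with a true effect of 15, 1,450 were significant at f = 0.10 and 1,442 at f = 0.20. None tipped between 0 and −10. At +10, 35 and 95 had tipped (2.4% and 6.6%).

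**6. Check with multiple imputation.** In one constructed data set with 5 of 50 cenegermin values imputed, 200 imputations and Rubin's rule, p on the Table 3 sign was 0.0175 at Δ = 0, 0.0091 at −10 and 0.0329 at +10. On the reduction sign the values at −10 and +10 swapped.

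**The case against.** The strongest reply is that SAP 10.1.1 does give a sign. It labels the SANDE change a reduction in both the null hypothesis and the definition of μ, and the alternative makes larger values better. On that reading the grid is adverse for both endpoints, and Table 3 is only a generic rule. The instruction that each shift be a worse effect could also lead a careful programmer to the right direction, and the required plot would show p falling where it should rise.

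Part of this stands. The SAP is not silent on sign, and the intent is clear. But 10.1.1 states a hypothesis. The shift is applied to imputed values, which 10.1.2.2 says are scores. Table 3 covers every change variable without exception, and the code places AVAL beside raw SANDE scores. Someone following the written steps would go the wrong way, and relying on the programmer to notice is not pre-specification.

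It is also fair that, at the design effect, neither sign usually produces a tip within 10 points, so the sign error alone alters the reported result mainly for narrowly significant outcomes. Those are the outcomes for which the analysis matters most, and the short range is a further reason to revise the grid. The sizes of the corrected tipping shifts depend on the assumed imputed fraction and on how variance is treated: holding the SE at 4.0 with a normal test gives +71.6 instead of +57.0 at 15 points with 10% imputed. The direction does not depend on either.

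**Conclusion.** The concern holds: the SANDE tipping-point analysis is wrong as written. One grid serves two endpoints of opposite direction. On both scales that the SAP actually derives for SANDE the shifts favour cenegermin, and 10.1.1 conflicts with Table 3 without being reconciled.

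The consequence is limited to a sensitivity analysis for one co-primary endpoint. A result at 8.5 points that would tip at a shift of about 3 to 6 points would be shown as never tipping. Alpha and power do not change, and the MAR, complete-case and per-protocol analyses remain. The SANDE hypothesis should be put on the same sign, because under Table 3 its inequality would literally point to the wrong tail.

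The figures assume 50 per arm, SD 20 and 10% or 20% of cenegermin values imputed. The closed-form results ignore between-imputation variance, covariates and the upper limit of the scale. Confidence in the direction is high. This should be fixed.

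**What to change.** In this order:

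1. **Settle the coding.** In SAP 10.1.2.2 and 15.5.2, define the SANDE AVAL as the week-12 global score, or as post-baseline minus baseline. With baseline SANDE in the model as a covariate, both give the same treatment difference. In 10.1.1, either write μ explicitly as mean baseline minus week 12 or reverse the inequality, so that it agrees with Table 3.
2. **Separate the grids in 10.1.3.** Keep Δ from 0 to −10 for Schirmer. For SANDE, add Δ ≥ 0 to the imputed cenegermin values and extend until p ≥ 0.025 or the scale limit is reached, with the resulting week-12 score capped at 100. If the sponsor codes AVAL as a reduction instead, the SANDE shift must stay negative, so step 1 has to come first.
3. **Define the tipping point** as the smallest absolute Δ with p ≥ 0.025, since the smallest Δ is ambiguous on a negative grid. If the limit is reached, report that there is none within the scale.

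The cost is a short SAP edit (10.1.1, 10.1.2.2, 10.1.3 and 15.5.2) and a changed program loop, made before unblinding. No new data are needed.
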